9.3. Blood Sampling for Drug Removal

Blood samples for the analysis of plasma apixaban and rivaroxaban concentrations will be collected at the times indicated in the Schedule of Assessments in [Appendix 4](#) and will be stored until analysis. A pre-CPB sample will be obtained prior to the start of CPB and may be performed up to 2 hours prior to skin incision. While the subject is on CPB, serial samples will be drawn at 30-minute intervals following initiation of CPB, through the first 2 hours of CPB. Sampling times will be at 30 (± 15) minutes, 60 (± 15) minutes, at 90 (± 15) minutes, and at 120 (± 15) minutes of CPB time. A post-CPB sample will be obtained as soon as possible following the end of CPB, and no later than 30min after the subject has been disconnected from the CPB circuit.

If the total CPB time required for the procedure is <120min (2hrs), the serial sampling will only be performed through the required duration of CPB. For procedures requiring >120min (2hrs) of CPB time, serial sampling will **not** extend beyond this time point, as the incremental change is expected to be minimal compared to the post-CPB value. Processing, storage, and shipping instructions for these blood samples will be provided by the Sponsor (or designee) to the investigation sites and detailed in the Study Laboratory Manual. Samples will be stored and analyzed at a designated bioanalytical laboratory using a validated assay. Any residual samples will be destroyed at the completion of the final investigation report or if the subject withdraws assent/consent to use the sample for the research purposes of the investigation.

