The primary effectiveness endpoint will be evaluated using the Win Ratio method of analysis for a hierarchical composite endpoint based on the Finkelstein-Schoenfeld test (Finkelstein and Schoenfeld, 1999; Pocock, et al., 2012) with three components: a) fatal bleeding events occurring within 48hrs of the index procedure, b) moderate, severe, or massive bleeding based on the Universal Definition of Perioperative Bleeding in Cardiac Surgery (UDPB) ≥ 2 classification, and c) 24-hour chest tube drainage (volume, mL). The Win Ratio assigns “wins”, “losses”, or “ties” between randomized groups in a serial fashion across all components of the composite endpoint adhering to the declared hierarchical order from higher to lower clinical importance.[14] [15] A ratio of “wins” greater than 1.0 favors the treatment arm; when the lower bound of a 95% confidence interval (CI) around the ratio exceeds 1.0, the treatment is shown to be statistically superior to control at alpha = 0.05. The primary effectiveness analysis will be performed in the overall study population comprised of both apixaban and rivaroxaban patients to evaluate the difference between the SOC (control) arm and the DrugSorb-ATR (investigational) arm.

The key secondary effectiveness endpoints are the pre-CPB vs. post-CPB change in drug levels (apixaban and/or rivaroxaban) measured by liquid chromatography/tandem mass spectrometry (LC/MS-MS) [drug removal endpoint]. Change in each subject's blood concentration of apixaban or rivaroxaban from immediately *before* to immediately *after* CPB will be collected and analyzed by a central core laboratory. Drug removal will be analyzed for apixaban and rivaroxaban independently.

Change from baseline in blood concentration of apixaban or rivaroxaban is defined as:

$$\frac{\text{pre-CPB [apixaban]}_{\text{blood}} - \text{post-CPB [apixaban]}_{\text{blood}}}{\text{pre-CPB [apixaban]}_{\text{blood}}} * 100\%$$

or

$$\frac{\text{pre-CPB [rivaroxaban]}_{\text{blood}} - \text{post-CPB [rivaroxaban]}_{\text{blood}}}{\text{pre-CPB [rivaroxaban]}_{\text{blood}}} * 100\%$$

Based on existing benchtop evidence, a conservative estimate of 40% reduction in blood concentration of DOAC between pre- and post- DrugSorb-ATR removal is expected, with a standard deviation of 40%, in the treatment arm. Minimal change is expected in the control arm. A two-sample t-test will be used to evaluate the difference between treatment arms.

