9.1. Procedures and Assessments by Study Phase

Subjects are considered enrolled in the study at the time which consent or assent (in the case of a proxy providing permission for an incapacitated subject) to participate in the study is provided. Details on the consent process are provided in [Section 15.3](#) and the ethics of consenting non-vulnerable and vulnerable (incapacitated) populations are detailed in [Appendix 3](#).

[figure not shown]
Subjects who do not meet study entry (inclusion/exclusion) criteria are screening failures and will exit the study. Treated subjects will be followed up through 30 days after the surgical procedure.

The start of the investigation is defined as the date of consent to enroll the first prospective subject. The end of the investigation is defined as the date of the last subject's last contact or assessment (whether scheduled or unscheduled).

The investigation is divided operationally into 6 phases:

- Screening Phase – the period between the time consent/assent is provided for study participation and the start of the surgical procedure with CPB
- Pre-CPB Phase – the period within 2 hours before start of the operation with CPB (time of skin incision). *Note: The Pre-CPB Phase may overlap with the Screening phase.*
- Operation Phase – the start of the surgical procedure (defined as skin incision) until chest closure.
- Post-CPB Phase – the period from the end of CPB up to admission to the Intensive Care Unit (ICU). *Blood sampling for drug removal obtained in the post-CPB phase should be drawn as soon as possible following the end of CPB, and no later than 30min after the subject has been disconnected from the CPB circuit.*
- Post-operation Phase – from admission to the ICU through Day 29 or the point of discharge from hospitalization, whichever is sooner. **Discharge from hospitalization** means the date of initial discharge from the hospital in which the cardiothoracic surgery was completed (i.e., index procedure) irrespective of discharge to home care, secondary care or other rehabilitation unit.
- Day 30 Evaluation Post-Cardiothoracic Surgery – The subject status on postoperative day 30 will be evaluated by telephone contact, in-person follow-up visit, or review of medical records. Assessment of mortality (i.e., vitals status), blood product transfusions, and other adverse events will be performed.

An overview of the investigation design is shown in [Figure 5](#).

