9.1.2. Operation Phase

The Operation Phase will be initiated at the time of first incision. During the Operation Phase, the subject will either undergo standard CPB, or CPB + DrugSorb-ATR according to randomization.

Subjects randomized to the control arm will receive standard of care in which a sham device will be in place parallel to the CPB circuit, but through which no blood will circulate. Refer to [Section 6.3](#) for details.

In the treatment arm, DrugSorb-ATR treatment will initiate with the start of CPB and continue through the end of CPB. Per the IFU and under the guidance of a Field Clinical Specialist, the DrugSorb-ATR cartridge will be placed into a parallel bypass circuit to the main blood flow in a standard CPB circuit and primed for use in preparation for the Operation Phase. Throughout the treatment session, the DrugSorb-ATR setup will be monitored for blood leaks, flow changes, and/or clots. Any adverse device events and/or device observations must be recorded by indicating the location of leaks and/or by recording the size of any clots present. DrugSorb-ATR treatment flow rates will be controlled utilizing a roller clamp placed on the distal, superior line above the DrugSorb-ATR prior to returning to the reservoir. Flow rate will be measured using a Sponsor provided Transonic® (or equivalent) ultrasonic flow meter and probe, placed on the inlet line below the DrugSorb-ATR device. **The blood flow rate through the device will be adjusted to 500mL/min ± 100mL/min.**

During the operation phase, arterial blood gas analysis will be obtained at the following time periods: within 30min pre-CPB, 30 ± 15 min into CPB, within 30 minutes post-CPB, and upon admission to the ICU. Activated clotting time will be obtained once at 30 ± 15 minutes into CPB, and once *within 30 minutes* post-protamine administration. All other assessments including monitoring of transfusions, will be performed as detailed in [Table 6 of Appendix 4](#). Intraoperative transfusions will be administered at the discretion of the investigator in accordance with standard institutional practice.

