Benchtop studies of drug removal by DrugSorb-ATR (data on file, CytoSorbents Corporation) demonstrate concentration and time dependent absolute drug removal, which are nearly identical for both apixaban and rivaroxaban. Based on these benchtop studies, a conservative estimate of 40% reduction in blood concentration of DOAC between pre- and post- DrugSorb-ATR removal is expected, with a standard deviation of 40%, in the treatment arm. Minimal change is expected in the control arm. A two-sample t-test will be used to evaluate the difference between treatment arms. Due to highly variable baseline drug levels in the study population, percent change from baseline will be analyzed as opposed to observed values.

Additional secondary endpoints include 24-hour CTD (volume [mL]), total platelet transfusions during the index hospitalization (volume [mL] and units), and total PRBC transfusions during the index hospitalization (volume [mL] and units). Twenty-four-hour CTD (mL) will be assessed via two-sample t-test for mean difference. In the event the assumptions for a two-sample t-test are not met, a nonparametric test such as a Mann-Whitney test will be employed, with median and range values provided in the output. An additional analysis of 24-hour CTD will compare the frequency of subjects falling into volume categories (i.e., <500 mL, 500 to <750 mL, 750 to <1000 mL, 1000 to <1250 mL, 1250 to <1500 mL, and ≥ 1500 mL), and will use a Fisher-Freeman-Halton exact test to compare treatment groups. The transfusion endpoints will all be analyzed using two-sample t-tests for mean differences, and Fisher-Freeman-Halton exact tests for units. In the event the assumptions for a two-sample t-test are not met, a nonparametric test such as a Mann-Whitney test will be employed, with

median and range values provided in the output. The remaining Win Ratio component parts will also be included as secondary endpoints: proportions of fatal perioperative bleeding events will be assessed via Fisher's exact test; and proportions of UDPB events (by category) will be assessed via a Fisher-Freeman-Halton exact test. All surgical re-exploration for excessive bleeding, including those events occurring beyond the timeframe captured within the UDPB component of the primary endpoint will be captured as a secondary endpoint. Time to re-exploration will be considered.

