Activated Clotting Time (ACT) ^k			X	X							
Arterial Blood Gas (ABG) ^l			X	X	X						

Study Procedures	Screening	Pre-CPB	Operation	Post-CPB	Post-Operation					Follow-up Visit/End of Study/Early Termination	
Timepoint	Up to 36 hours before Operation	Within 2 hours before start of operation (i.e., skin incision)	From chest incision to chest closure	Within 30min after end of CPB	ICU Admission	POD 1	POD 2	POD 3	POD 4	POD 5-29	POD30 + 5 days
Blood products ^m		X-----		X-----	X	X	X	X	X	X ^s	
Operation blood loss and drainage ^m			X								
Post-Operation chest tube drainage				X-----	X						
Post-Op blood loss & bleeding ^m					X	X	X	X	X	X ^s	X
Daily assessment						X	X	X	X	X ^s	
Adverse events ⁿ	X	X	X	X	X	X	X	X	X	X	X
Ventilation and mechanical support ^o					X	X	X	X	X	X ^s	
FiO2 ^p					X	X	X	X	X	X ^s	
Vasopressor requirements ^q					X	X	X	X	X	X ^s	

Abbreviations: AE = adverse event; CPB = cardiopulmonary bypass; D = day; h = hour; eCRF = electronic case report form; ICF = Informed Consent Form; ICU = Intensive Care Unit; POD = post-operative day; SOC = standard of care.

^a Authorization or informed consent must be obtained at Screening (see [Appendix 3](#))

^b Body mass index will be calculated from the subject's height and weight measurements obtained at Screening or from the values in the medical record in the current hospital admission.

^c Pre-randomization stratification will be performed based on the *planned* surgical procedure; changes in the planned surgical procedure should be updated within the IxRS system whenever possible to avoid any unintended protocol deviation.

^d Blood samples will be collected for the determination of plasma DOAC concentration at a designated bioanalytical laboratory using a validated assay. The pre-CPB blood sample will be drawn prior to the start of cardiopulmonary bypass and can be up to 2hrs prior to skin incision. The post-CPB blood sample will be drawn as soon as possible following the end of CPB, and no later than 30min after the subject has been disconnected from the CPB circuit. During the procedure, while the subject is on CPB, serial sampling will be obtained q30±15min up through 2hrs of CPB. If the procedure requires a CPB time of <2hrs, then sampling will be q30±15min only up through completion of the CPB.

^e Baseline EKG is required on file within the subject's medical record pre-op but does not need to have been performed within 36hrs of surgery.

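### The baseline drug sample may be drawn hours before bypass starts, so washout before bypass enters the percent-change endpoint and biases the estimate of device removal

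*Combined protocol and SAP*

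**What the plan says.** Section 9.3 sets the sampling rule: "A pre-CPB sample will be obtained prior to the start of CPB and may be performed up to 2 hours prior to skin incision". Footnote d of Table 6 (Appendix 4) repeats it: "The pre-CPB blood sample will be drawn prior to the start of cardiopulmonary bypass and can be up to 2hrs prior to skin incision". Section 9.1 anchors the Pre-CPB Phase to incision as well: "the period within 2 hours before start of the operation with CPB (time of skin incision". The other end of the interval is tight (Section 9.3): "A post-CPB sample will be obtained as soon as possible following the end of CPB, and no later than 30min" after disconnection.

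The Synopsis (Statistical methods, Effectiveness Analysis) describes the key secondary endpoint as the change "from immediately *before* to immediately *after* CPB". Other places are looser. Sections 4.3.2 and 11.3 say only pre-CPB versus post-CPB. Section 1.5 places the first samples in the pre-operative period. The key secondary paragraph of Section 3 speaks of preoperative and postoperative concentrations.

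On analysis, Section 11.3 says that "percent change from baseline will be analyzed as opposed to observed values". It compares the arms by a two-sample t-test, expects a 40% reduction with an SD of 40% under treatment, and expects little change in controls. No term for elapsed time is described.

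A blood draw close to CPB already exists. Section 9.1.2 says that "arterial blood gas analysis will be obtained at the following time periods: within 30min pre-CPB".

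**The concern.** The permitted gap between the baseline draw and the start of CPB is 2 hours plus the time from incision to CPB. A site can comply fully with Section 9.3 and still not measure the quantity the Synopsis defines. Whatever drug is cleared in that gap is counted in the change across CPB.

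It is natural to think that this cancels because it happens in both arms. On a percent-change scale it does not. Washout before CPB multiplies what is left for the device to remove, so subtracting one arm from the other leaves a shrunken difference.

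Two things are at stake. First, Section 3 gives these endpoints the job of quantifying how much drug the device removes and of linking removal to less bleeding, so the estimate matters as well as the p-value. Second, Section 11.3 tests apixaban and then rivaroxaban directly after the primary endpoint. A miss on either one blocks chest tube drainage, platelet and PRBC claims.

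**Working it through.** **The plan's own figure.** Section 11.1 gives 96.3% power for each drug, with 29 versus 29 subjects, a 40-point difference, SD 40, and an equal-variance t-test at two-sided 0.05. The noncentrality is 40 / (40 × √(2/29)) = 3.81 on 56 degrees of freedom. Noncentral-t power is 96.26%, so the figure reproduces.

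**Model.** Let r be the ratio of the post-CPB level to the level at CPB start. The plan's assumptions correspond to a mean r of 0.6 under treatment and 1.0 in controls, with SD 0.40. Let w be the fraction of the baseline level still present when CPB starts. Under first-order decline, w = 0.5^(gap / half-life). The recorded percent change is 100 × (1 − w × r), so:

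- control mean = 100 × (1 − w)
- treatment mean = 100 × (1 − 0.6w)
- arm difference = 40 × w
- SD = 40 × w if w is common to all subjects

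**Assumed inputs (not in the documents).** Half-life 5 to 12 h; gap from baseline draw to CPB start 1 to 3 h. Rounded results:

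| Half-life (h) | Gap (h) | w | Control change | Treatment change | Difference (points) | Power, SD fixed at 40 | Power, SD = 40w |
|---|---|---|---|---|---|---|---|
| none assumed | 0 | 1.000 | 0% | 40% | 40 | 96.3% | 96.3% |
| 12 | 1 | 0.944 | 5.6% | 43.4% | 37.8 | 94.2% | 96.3% |
| 12 | 3 | 0.841 | 15.9% | 49.5% | 33.6 | 88.2% | 96.3% |
| 8 | 2 | 0.841 | 15.9% | 49.5% | 33.6 | 88.2% | 96.3% |
| 8 | 3 | 0.771 | 22.9% | 53.7% | 30.8 | 82.3% | 96.3% |
| 5 | 1 | 0.871 | 12.9% | 47.8% | 34.8 | 90.3% | 96.3% |
| 5 | 3 | 0.660 | 34.0% | 60.4% | 26.4 | 69.5% | 96.3% |

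The last row in full: w = 0.5^(3/5) = 0.660 and 40 × 0.660 = 26.4. With SD 40 the noncentrality is 3.81 × 0.660 = 2.51, which gives 69.5%. With SD 26.4 the noncentrality is 3.81 again, which gives 96.3%.

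**Gaps that vary by subject.** A simulation of 40,000 trials used gaps of 0.5–3.5 h and half-lives of 5–15 h, with the spread following the model. It gave a mean change of 48.4% under treatment and 13.8% in controls, a difference of 34.6 points, a within-arm SD of about 35, and power of 95.8%. With no device effect, the rejection rate was 4.9%.

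**Log scale.** log(post/pre) = log w + log r. If w has the same distribution in both arms, as randomisation should ensure, log w cancels and the arm difference reflects r alone.

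**The case against.** A reader might infer that the plan loses power to somewhere between 70% and 94%. The documents do not support that. Those figures shrink the mean difference by w but hold the SD at 40. In the same model w also multiplies the spread, and power then hardly moves, even when the gap varies between subjects. A fixed SD would need most of the variance to be independent of w, for example assay error, and nothing in the documents shows that. The 70% end also needs every subject to have a 3 h gap and a 5 h half-life, whereas 2 hours before incision is an outer limit. Section 11.3 moreover calls the 40% reduction conservative.

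A reader might also infer that the trial credits natural washout to the device. In the between-arm test it does not. Washout occurs in both randomised arms, the test keeps its type I error, and the device effect is understated. Only the within-arm percentage is inflated.

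Two further points stand in part. The wording about immediately before CPB appears in one Synopsis sentence, while the incision-anchored window in Sections 9.1, 9.3 and Table 6 looks deliberate. That makes reconciliation necessary but does not say which quantity is meant. A wide window may also protect against a missing baseline in urgent surgery, which is a good reason to keep an earlier sample as a back-up.

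The direction of the bias is not certain for every subject either. Someone still absorbing a recent dose could have w above 1.

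**Conclusion.** The point holds as an inconsistency in the definition with a predictable bias in estimation. With baselines drawn under the current rule, the arm difference in percent change is 40 × w instead of 40, within-arm removal is overstated, and control change is not minimal as Section 11.3 expects. Over half-lives of 5–12 h and gaps of 1–3 h, control loss is about 6–34%, treatment-arm change is about 43–60%, and the difference is about 26–38 points. These sizes rest on first-order decline and on two inputs the documents do not give.

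The plan's own background treats washout as material. Section 3 judges the apixaban case report against expected natural washout, although Section 1.3 places that patient's first level at CPB initiation.

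No loss of test validity follows, and no loss of power is demonstrated. Power lies between about 96% (SD scaling with w) and about 70% (fixed SD, worst corner). The case for change is that the trial should measure the removal it says it will quantify, and can do so at very little cost.

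**What to change.** 1. Reconcile the baseline timing across the Synopsis, Sections 1.5, 3, 9.1 and 9.3, and Table 6 footnote d, so that one definition governs the endpoint.
2. Make the baseline the drug sample drawn with the arterial blood gas that Section 9.1.2 already requires within 30 minutes before CPB.
3. Use an earlier sample only as a flagged back-up when that draw is missed.
4. Use the clock times of both samples and of CPB start in the analysis. The trapezoidal AUC in Section 11.5 needs sample times, so they may already be captured; the Laboratory Manual was not available to confirm this.
5. Prespecify a sensitivity analysis of log(post/pre) with the elapsed time from baseline draw to CPB start as a covariate, including a rule for post-CPB values too low to quantify.

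The cost is revised wording in the protocol and Laboratory Manual, slightly tighter sampling logistics before CPB, and an extra tube for subjects in whom a back-up is drawn. No visit is added and the sample size does not change. With the gap near zero, the planned 40-point difference and 96.3% power apply as stated.

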10. CONCOMITANT MEDICATIONS

Medication history and concomitant medications will be recorded in the eCRF. The medication history will include all acute and chronic prescription and over-the-counter medications taken during the 30 days prior to Screening. Medication history will be repeated on the day of the procedure if different from the day of screening.

All medications administered during the Screening, Pre-CPB, Intraoperative, Post-CPB, and during the Postoperative Phases must be collected. Unless medically necessary, concomitant medications should be withheld two hours prior to and during therapy with the investigational device. This is to reduce risk of unintended removal and inadequate delivery of these medications.

Study subjects may, in addition to apixaban and rivaroxaban, also be receiving other antithrombotic medications during their current hospitalization that could contribute to bleeding. The use of antithrombotic medications will be reviewed during the screening period. Certain agents and the timing of administration could confound the results of the study and are therefore listed as prohibited medications (see [Appendix 5](#) for details). Subjects on prohibited medications at the time of surgery cannot be randomized. Each antithrombotic medication is categorized as allowed or prohibited in the study, and the reason for this categorization is provided.

Prior and concomitant medications will be coded using the latest version of the WHO Drug Dictionary, based on Anatomical Therapeutic Chemical classification and Preferred Name.

There are no protocol-specified prohibited medications during the Postoperative phase of the study.

